8.1.9. Clinical Laboratory Assessments

See Appendix 1 for the list of clinical laboratory tests to be performed and refer to the Schedule of Activities (Section 1.3) for the timing and frequency.

The Investigator must review the laboratory report, document this review, and record any AEs per the guidance in Appendix 6. The laboratory reports must be filed with the source documents.

Shifts of clinically significant Grade 3 or Grade 4 laboratory abnormalities or any clinically significant laboratory abnormalities considered possibly related to study drug in the opinion of the Investigator should be repeated within 48-72 hours and followed to resolution or until stable.

All protocol-required laboratory assessments, as defined in Appendix 1, must be conducted in accordance with the laboratory manual and the Schedule of Activities.

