3.8. Visits

3.8.1. Windows

In data listings, the relative study day of all dates from first dose will be presented.

Scheduled visit assessments will be determined based on a two-step process using the parameters of exposure to study drug and scheduled visit assessment windows.

Step 1:

• The last dose date (maximum from dates of discontinuation form and exposure data) must be within 14 days, inclusive, of the last assessment of those within the treatment exposure period (12 weeks). If the last dose date is after or within 14 days inclusive of the Week 12 assessment there will be an assumption that all previous assessments were performed while under proper drug exposure. Any assessments performed greater than 14 days of the last dose date will be considered unscheduled irrespective of Table 4 mapping.

Step 2:

- Use Table 4 to initially map the appropriate assessment under consideration
- For multiple assessments mapped to the same scheduled visit interval, select the assessment date that is closest to the target day of the visit window in terms of absolute difference, irrespective of scheduled or unscheduled visit type. Any assessment not selected in the window is considered unscheduled.

In the event of a scheduled visit assessment tie AND the assessment was performed as an original scheduled assessment select this over an unscheduled; if both assessments are unscheduled or scheduled select the first assessment, then classify the other as unscheduled.

Final, Version 2.0, 26JULY2023

CONFIDENTIAL

Labcorp Drug Development Study: 000000231152 Protocol Reference: TERNCB-2002

Table 4 Treatment Period Visit Windows

Target Scheduled Visit	t Scheduled Visit Target Study Day ^a Analysis Window Study Day ^a		
	•	Low	High
Targeted physical examina	ation, vital signs, EC	CG, chemistry and hema	atology labs
Baseline	1	See Section 3.6.2	
Week 2	15	2	22
Week 4	29	23	36
Week 6	43	37	50
Week 8	57	51	70
Week 12	85	71	99
Thyroid axis testing	•		·
Baseline	1	See Section 3.6.2	
Week 2	15	2	29
Week 6	43	37	50
Week 12	85	71	99
Weight, MRI-PDFF, MRI	-cT1, and fibrosis b	iomarkers	·
Baseline	1	See Section 3.6.2	
Week 6	43	29	57
Week 12 ^b	85	71	99
Week 16	For all		
	parameters, use nominal visit as		
	recorded on CRF.		

a Study Day will be calculated from first dose of study drug. Visit windows defined by the low and high values are inclusive.

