8.3. Clinical Safety Laboratory Evaluations

All laboratory assessments are specified in Appendix 1 of the study protocol. Laboratory parameters will be summarized in conventional units. Coagulation parameters, hemoglobin A1c, direct bilirubin, and indirect bilirubin will not be summarized.

Quantitative clinical chemistry, hematology, and urinalysis results will be summarized by treatment group using descriptive statistics at baseline and at each post-baseline visit. The change and percent change from baseline will also be summarized.

Additional summaries will be provided by scheduled visits for the number and percentage of patients with

- Total CK > 5x ULN
- Hg < 10 mg/dL
- HCT < 30%
- platelets < 100,000 /microL
- WBC < LLN

All clinical safety laboratory data will be presented in by-patient data listings. A separate listing for central laboratory normal ranges, by lab category, lab test, lab parameter, sex, and age, will be presented.

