8.3.5. Shifts in Normal Range

Shift tables for each laboratory test (hematology, chemistry, and urinalysis) showing the shift from normal at baseline to abnormal at each post-baseline visit will be presented by visit. Summaries will present the number and percentage of patients with shifts by treatment group. Denominators for percentages will be the number of patients with non-missing data at the specific assessment and baseline.

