8.5. Electrocardiograms

Summary statistics will be provided for heart rate, PR interval, QRS interval, QT interval, and QTcF at each visit. The investigator interpretation is collected as normal, abnormal not clinically significant (NCS), or abnormal clinically significant (CS). Patients whose interpretation shifts from normal to abnormal (CS or NCS) will be listed separately including description of the abnormality and any associated comments.

Categorical summaries will for baseline, worst post-baseline, and change from baseline for the following QTcF values will be presented:

- > 450 msec
- > 480 msec
- > 500 msec
- Change from baseline > 30 msec
- Change from baseline > 60 msec

CONFIDENTIAL

All ECG results will be presented in by-patient data listings. If applicable, cardiologist consult information will be presented in a separate by-patient data listing.

CONFIDENTIAL

9. Other Assessments

Other assessments will be provided in by-patient data listings only; no summary tables will be provided, including but not limited to the following:

- Eligibility details including unmet eligibility criteria
- Informed consent
- Randomization schema
- Physical examination collection information
- Serology
- Pregnancy testing
- FSH test
- Urine drug screen
- Alcohol test
- Urinalysis and Urine Microscopic Examination
- Coagulation
- Hemoglobin A1c
- Direct bilirubin
- Indirect bilirubin
- Laboratory reference ranges
- Cardiology consult
- Overdose
- Comments

Final, Version 2.0, 26JULY2023

CONFIDENTIAL

10. Changes to Protocol Planned Analyses

There were no changes from the protocol planned analyses.

CONFIDENTIAL

Statistical Analysis Plan CONFIDENTIAL Labcorp Drug Development Study: 000000231152 Protocol Reference: TERNCB-2002

11. Appendices

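### Abnormal laboratory values that are displaced by a repeat, or seen only at unscheduled draws, are left out of the SAP 8.3 threshold counts and the 8.3.5 shift tables

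*SAP*

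**What the plan says.** **Selection within a window.** SAP 3.8.1, Step 2, maps assessments to the windows of Table 4. If more than one falls in a window, it selects the one "closest to the target day of the visit window in terms of absolute difference, irrespective of scheduled or unscheduled visit type". The others lose their visit label: "Any assessment not selected in the window is considered unscheduled". A tie goes to the planned draw: if "the assessment was performed as an original scheduled assessment select this over an unscheduled".

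**What uses the selected value.** For CK, haemoglobin, haematocrit, platelets and WBC, SAP 8.3 states: "Additional summaries will be provided by scheduled visits for the number and percentage of patients with" values beyond listed cut-offs. SAP 8.3.5 plans shift tables for haematology, chemistry and urinalysis, "showing the shift from normal at baseline to abnormal at each post-baseline visit will be presented by visit".

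**When repeats are drawn.** Protocol 8.1.9 says that clinically significant Grade 3 or 4 shifts, and clinically significant abnormalities possibly related to study drug, "should be repeated within 48-72 hours and followed to resolution or until stable". Protocol Appendix 3 asks for liver-test repeats within 48 hours once its monitoring criteria are met. The opening of Protocol section 8 also allows repeats for technical problems with a sample.

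**Other outputs.** SAP 8.3.1 counts patients with a CTCAE rise of at least 2 grades, and separately of at least 1 grade, after baseline through Week 16. Its Table 11 counts patients meeting liver-test criteria. Neither is described as by visit. For the ECG, SAP 8.5 plans: "Categorical summaries will for baseline, worst post-baseline, and change from baseline for the following QTcF values".

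**The concern.** Many repeat samples are taken because the first result was abnormal. A rule that ignores why a sample was drawn, and looks only at its distance from the target day, can put the repeat in the visit's place and move the result that prompted it out of the by-visit data. Separately, an abnormality found only at an unscheduled draw has no place in a by-visit table if the scheduled value lies nearer the target day.

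At stake are two safety outputs: how many patients in each arm reached the listed CK and haematology cut-offs, and how many moved from normal to abnormal. With about 20 patients per arm, one or two omitted patients would visibly change a percentage (1 of 20 is 5 percentage points).

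**Working it through.** The plan states no figure here, so there is none to reproduce. The check is an enumeration of the Step 2 rule.

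**Inputs**
- Visit margin through Week 12: 3 days either side (Protocol Schedule of Activities).
- Repeat lag: 2 or 3 days (Protocol 8.1.9); up to 2 days for liver tests (Protocol Appendix 3).
- Chemistry and haematology windows, target day (low to high), from SAP Table 4: 15 (2 to 22), 29 (23 to 36), 43 (37 to 50), 57 (51 to 70), 85 (71 to 99).

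**Rule.** Let the scheduled draw fall at target + d and the repeat r days later. The repeat is selected only if |d + r| < |d|; a tie keeps the scheduled value. For r > 0 this means d < 0 and r < 2|d|.

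**Both draws share a window.** The extremes for r up to 3 are d = −3 and d + r = 3 + 3 = +6. Every window reaches at least 6 days before and 7 days after its target, so the result is the same at all five visits.

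| Visit offset d | r = 1 | r = 2 | r = 3 |
|---|---|---|---|
| −3 | 2 < 3, repeat | 1 < 3, repeat | 0 < 3, repeat |
| −2 | 1 < 2, repeat | 0 < 2, repeat | 1 < 2, repeat |
| −1 | 0 < 1, repeat | 1 = 1, scheduled | 2 > 1, scheduled |
| 0 to +3 | scheduled | scheduled | scheduled |
| Displaced | 3 of 7 | 2 of 7 | 2 of 7 |

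For the 2- and 3-day lags together, 4 of 14 combinations displace the scheduled value. At r = 4 or 5 only d = −3 is affected (1 of 7); at r = 6 or 7 none is. Visits more than 3 days early but still inside the analysis window are exposed by the same inequality.

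**Hypothetical displacement.** Week 12 visit on Day 82 with CK above 5 times ULN, repeat on Day 84 below it. The distances from Day 85 are 3 and 1. Day 84 becomes Week 12, and the Day 82 value is not counted.

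**Hypothetical unscheduled-only peak.** Week 4 visit on Day 29 with normal platelets, unscheduled draw on Day 33 below 100,000. The distances are 0 and 4. Day 29 is kept, and no early visit is needed for this loss.

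**Direction of the patient count.** The selected values are a subset of all post-baseline values. So the patients who ever cross a cut-off on selected values are a subset of those who ever cross it on any value. Equality is possible; overstatement is not.

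**With thresholds counted on any post-baseline value:** 0 of 14 combinations lose the abnormal scheduled value.

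**The case against.** The strongest reply is that the plan does not rely on these two outputs alone. SAP 8.3.1 counts patients with grade rises of at least 1 and at least 2, and Table 11 counts patients meeting liver criteria, neither with a by-visit limit. A shift to Grade 3 or 4, which is one trigger for the 48-72 hour repeat, is a rise of at least one grade and would be counted in 8.3.1 if all values are used. Every value is also listed by patient. By-visit laboratory summaries follow Protocol 9.4.5, and nearest-to-target selection with a stated tie rule is a legitimate pre-specified choice.

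Much of this stands. A reader might infer that safety peaks disappear from the tables altogether; the documents do not support that. The reply does not close the gap, however. Table 11 covers only ALT, AST, ALP and bilirubin. SAP 8.3.1 measures change in grade, not the 8.3 cut-offs. Neither says whether unscheduled values are included, although the SAP says so explicitly for laboratory baselines (3.8.2) and for the carried-forward primary endpoint (7.2). Listings give no incidence by arm. The QTcF comparison is helpful but limited, since SAP 8.5 does not mention unscheduled ECGs either.

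**Conclusion.** The point holds for two outputs: the 8.3 threshold counts and the 8.3.5 shift tables omit abnormal values that are displaced or seen only at unscheduled draws. It is worth correcting, and it does not touch the primary endpoint.

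The day counts (2 of 7 for a 2- or 3-day lag, 3 of 7 for a 1-day lag) are not loss rates. The documents give no distribution of visit days, and the counts presuppose that a repeat was drawn. A patient leaves the ever-crossed total only if the repeat is back across the cut-off and no other selected value qualifies.

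Two further inferences should not be drawn:
- **That displacement always flatters the drug.** A repeat may be taken for technical reasons or may be worse than the first value; Appendix 3 orders liver repeats partly to see whether values are rising. Step 2 can also bring an unscheduled peak into a visit when it lies nearer the target. Only the patient-ever count is strictly one-sided.
- **That ALT response is inflated.** SAP 7.9 requires a fall of at least 17 U/L below baseline. The specific ALT repeat triggers are above 2 times baseline or above 5 times ULN. From above 2B, reaching B − 17 requires a drop of more than 2B − (B − 17) = B + 17 U/L between draws. The documents show no such effect, nor any effect on mean ALT change.

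**What to change.** Leave SAP 3.8.1 Step 2 unchanged. It also governs MRI-PDFF, cT1, weight and thyroid tests, and always preferring the scheduled sample could keep a faulty one over its valid repeat.

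1. **SAP 8.3:** beside the by-visit counts, add a row for patients meeting each CK, haemoglobin, haematocrit, platelet and WBC threshold at any post-baseline value through Week 16, including unscheduled and repeat tests.
2. **SAP 8.3.5:** add a worst-post-baseline column built from the same values, in the spirit of 8.5 for QTcF. For tests with both a lower and an upper limit, define the worst direction or show both.
3. **SAP 8.3.1 and Table 11:** state that all post-baseline values through Week 16 are used, including unscheduled and repeat tests.

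The cost is a few sentences and minor programming, with no new data. The added counts may look slightly less favourable than the by-visit ones.

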3.8.2. Definition of Baselines

The baseline value for statistical analyses of quantitative laboratory parameters is defined as the last non-missing assessment, including any unscheduled or repeat assessments, collected prior to the first administration of study drug, unless otherwise specified.

For glucose and lipid parameters, only assessments taken while fasting for 8 hours will be included in the baseline derivation.

The baseline value for analyses of qualitative parameters (e.g., normal/abnormal) is defined as the last evaluation prior to the first administration of study drug.

Final, Version 2.0, 26JULY2023

CONFIDENTIAL

The baseline value for analyses of weight, body mass index (BMI), and electrocardiogram parameters is defined as the last evaluation prior to the first administration of study drug.

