Trough PD Sampling ^c		X	х	Х	х		х		Х	Refer to Appendix 2 for additional detail.
NASH/ Fibrosis Biomarkers ^c		х			х		х		х	Includes CK-18 (M30 and M65), ELF (PIIINP, TIMP-1, HA), and PRO-C3.
Intensive PK Sampling (PK/PD sub-study only)		х					Xi			Intensive PK sampling will be performed pre-dose and 1, 2, 4, 6, and 24 hours post the first dose of study drug on Week 0/Day 1, and at pre-dose and 1, 2, 4, 6, 24, 48, and 72 hours post last dose of study drug at Week 12. Patients should be instructed to hold their dose of study drug until after pre- dose and after 24-hour PK samples are collected. Refer to Appendix 2 for additional detail.
Intensive PD Sampling (PK/PD sub-study Only)		х					Xj			7α C4 and FGF19 will be collected at matching timepoints to Intensive PK sampling (above) except at Week 12 when 7α C4 and FGF19 will not be collected at 48 and 72 hours post dose. Refer to Appendix 2 for additional detail.
Clinical Laborator	y Procedure	es/Assessn	nents							
Patient Fasting	х	х	х	х	х	х	х	х	х	Patients must be in fasted state for at least 8 hours prior to blood collection and treatment administration, where applicable.

	Screening]	Freatmen	t Period ^f			Follow -Up ^b ET ^a		Notes	
Visit	Screening	Week 0	Week 2	Week 4	Week 6	Week 8	Week 12	Week 16			
Study Day		Day 1	15	29	43	57	85	113			
Schedule Window (days)	-42 days		± 3	± 3	± 3	± 3	± 3	-7 /+2		Patients discontinuing the study at any time for any reason (Early Termination) should complete the ET visit as soon as feasible and return for a Follow-Up visit 4 weeks (-7 days /+2 days) after the last dose of study drug.	
Chemistry ^e	x	x	x	x	x	x	x	x	X	Specific analytes are listed in Appendix 1. ALT and AST stability may be evaluated prior to randomization per Section 5. Increased monitoring criteria for elevated ALT and/or AST above 2×Baseline or above 5×ULN, and elevated ALP above 3×ULN are outlined in Appendix 3. A standard lipid test will be collected as part of the clinical chemistry at Screening to confirm eligibility (Appendix 1). During study treatment, lipid parameters for PD assessments listed in Table 9 of Appendix 2 will be collected and results will be blinded. HDL will remain unblinded and will be collected as part of clinical chemistry at all visits. Refer to Appendix 5 for the eGFR formula, to be calculated by central lab.	
Hematology ^c	х	Х	х	Х	Х	Х	Х	Х	x	Specific analytes are listed in Appendix 1.	

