5.3.2. Meals and Dietary Restrictions

Patients should arrive at the clinic fasting for assessments and dosing as defined in the Schedule of Activities (Section 1.1). This includes at least an 8-hour fast prior to the visit, during which food and drink is restricted. Water is allowed ad libitum.

Patients participating in the PK/PD sub-study at (Week 0/Day 1) and Week 12 should arrive at the clinic fasting (an 8-hour fast prior to the visit) and restrict food and drink until 2 hours post-

dose. Food and drink may resume after this timepoint. Patients participating in the PK/PD substudy do not need to be fasting for blood collection at Week 12: 48- or 72-hours post-dose.

Patients should refrain from consumption of grapefruit or grapefruit juice 2 weeks before Randomization and through the end of treatment (Section 6.6).

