7.3. Lost to Follow up

A patient will be considered lost to follow-up if he or she repeatedly fails to return for scheduled visits and is unable to be contacted by the study site.

The following actions must be taken if a patient fails to return to the clinic for a required study visit:

- The site must attempt to contact the patient and reschedule the missed visit as soon as possible, counsel the patient on the importance of maintaining the assigned visit schedule and ascertain whether or not the patient wishes to and/or should continue in the study.
- Before a patient is deemed lost to follow up, the Investigator or designee must make every effort to regain contact with the patient (where possible, 3 telephone calls and, if necessary, a certified letter to the patient's last known mailing address or local equivalent methods). These contact attempts should be documented in the patient's medical record.
- Should the patient continue to be unreachable, he/she will be considered to have withdrawn from the study.

Discontinuation of specific sites or of the study as a whole are addressed in Section 10.1.8 and Section 7.1.1.

8. Study Assessments and Procedures

Study procedures and their timing are summarized in the Schedule of Activities. Protocol waivers or exemptions are not allowed.

Adherence to the study design requirements, including those specified in the Schedule of Activities, is essential and required for study conduct.

All screening evaluations must be completed and reviewed to confirm that potential patients meet all eligibility criteria. The Investigator will maintain a screening log to record details of all patients screened and to confirm eligibility or record reasons for screening failure, as applicable.

Repeat or unscheduled samples may be taken for safety reasons or for technical issues with the samples.

If a patient requires home quarantine due to SARS-CoV-2 infection or exposure, or due to COVID-19 symptoms or other associated concern with attending an in-person study visit, in accordance with Section 6.8.1, home health care visits may be made available to continue study assessments in the patient's home where feasible, and/or remote visits via telephone, telemedicine, or other appropriate virtual communication may be substituted for a visit to the site.

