Appendix 2: Sample Collection for Pharmacokinetics and Pharmacodynamics

Table 8 presents a description of PK/PD sample requirements at each study visit and timepoint.

Week	Day	Timepoint	Sample Type
0	1	Pre-dose (All Patients)	 Patients in PK/PD sub-study TERN-501, TERN-101, and TERN-101 metabolite TRN-000971 PK samples (PK/PD sub-study) Lipid Panel, 7αC4, FGF19, bile acids, and SHBG PD samples (PK/PD sub- study) Patients not participating in PK/PD sub- study Lipid Panel, 7αC4, bile acids, and SHBG PD samples
		 Post dose at the following timepoints (PK/PD sub-study only): 1 hour ± 5 minutes 2 hour ± 15 minutes 4 hours ± 15 minutes 6 hours ± 15 minutes 24 hours ± 1 hour prior to dosing on Day 2 	 TERN-501, TERN-101, and TERN-101 metabolite TRN-000971 PK samples 7αC4 and FGF19 PD samples
2	15 ± 3	Pre-dose (All Patients)	 TERN-501, TERN-101, and TERN-101 metabolite TRN-000971 PK samples Lipid Panel, 7αC4, and SHBG PD samples
4	29 ± 3	 Pre-dose (All Patients – PD samples) One sample between 2 and 6 hours post dose (All Patients – PK samples) 	 Lipid Panel, 7αC4, and SHBG PD samples TERN-501, TERN-101, and TERN-101 metabolite TRN-000971 PK samples
6	43 ± 3	Pre-dose (All Patients)	 TERN-501, TERN-101, and TERN-101 metabolite TRN-000971 PK samples Lipid Panel, 7αC4, and SHBG PD samples
8	57 ± 3	Pre-dose (All Patients)	TERN-501, TERN-101, and TERN-101 metabolite TRN-000971 PK samples
12	85±3	Pre-dose (All Patients)	 Patients in PK/PD sub-study TERN-501, TERN-101, and TERN-101 metabolite TRN-000971 PK samples Lipid Panel, 7αC4, FGF19, bile acids, and SHBG PD samples

Table 8PK/PD Sampling Timepoints

			 Patients not participating in PK/PD substudy TERN-501, TERN-101, and TERN-101 metabolite TRN-000971 PK samples Lipid Panel, 7αC4, bile acids, and SHBG PD samples
		 Post dose at the following timepoints (PK/PD sub-study only): 1 hour ± 5 minutes 2 hour ± 15 minutes 4 hours ± 15 minutes 6 hours ± 15 minutes 24 hours ± 1 hour on Day 86 PK only: 48 hours ± 2 hours on Day 87 72 hours ± 4 hours on Day 88 	 TERN-501, TERN-101, and TERN-101 metabolite TRN-000971 PK samples 7αC4 and FGF19 PD samples (up to 24 hours ± 1 hour on Day 86 only)
ET	ET	• At the ET Visit, for all patients discontinuing the study at any time for any reason (Early Termination)	 TERN-501, TERN-101, and TERN-101 metabolite TRN-000971 PK samples Lipid Panel, 7αC4, FGF19, bile acids, and SHBG PD samples

PD Sample Collection

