7.18. Pharmacodynamic Analyses

The pharmacodynamic (PD) endpoints of SHBG, lipid panel, FGF19, 7α C4, and bile acids are collected at the timepoints shown in Table 8 of the protocol.

The change from baseline in SHBG, LDL-c, will be analyzed in the same manner as specified in Section 7.7 and pairwise comparisons in Section 7.6 using the efficacy analysis set.

Plasma concentrations for $7\alpha C4$, FGF19, and bile acids that are BLQ will be set to $\frac{1}{2} \times BLQ$. Plasma PD parameters will be computed for PD patients only. Plasma PD parameters for $7\alpha C4$ and FGF19 will be calculated from the individual plasma concentrations using a non-compartmental approach for Day 1 and Week 12. Day 1 will include pre dose and all post dose assessments prior to dosing on Day 2. Week 12 will include pre dose and all post dose assessments. The actual PD sampling times will be used for the PD analysis. If actual PD sampling times are missing, nominal times will be used. Table 1 below presents the plasma PD parameters to be calculated.

Final, Version 2.0, 26JULY2023

CONFIDENTIAL

Labcorp Drug Development Study: 000000231152 Protocol Reference: TERNCB-2002

Table 10 Plasma PD Parameters

Abbreviation	Parameter Definition
AUEC ₀₋₂₄	Area under the effect-time curve from time 0 to 24 hours postdose
RAUEC	Ratio of AUEC (Week 12) /AUEC (Day 1).
C_{\min}	For $7\alpha C4$ only, minimum observed plasma concentration, obtained directly from the plasma concentration-time profiles. In the case where multiple minimums are of equal magnitude, the earliest minimum concentration will be reported as C_{min} .
RC _{min}	For $7\alpha C4$ only, ratio of $C_{min (Week 12)}/C_{min (Day 1)}$.
C _{max}	For FGF19 only, maximum observed plasma concentration, obtained directly from the plasma concentration-time profiles. In the case where multiple peaks are of equal magnitude, the earliest peak concentration will be reported as C_{max} .
RC _{max}	For FGF19 only, the ratio of $C_{max (Week 12)} / C_{max (Day 1)}$.
t _{min}	For $7\alpha C4$ only, time of the minimum observed plasma concentration, obtained directly from the plasma concentration-time profiles. In the case where multiple minimums are of equal magnitude, the time of the earliest minimum will be reported as the t_{min} .

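### The SAP filters non-fasted glucose and lipid samples out of baseline but has no matching rule for post-baseline samples that break the protocol's fast

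*SAP*

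**What the plan says.** **Baseline.** SAP 3.8.2 takes the last non-missing pre-dose laboratory value, unscheduled and repeat draws included, and then adds: "For glucose and lipid parameters, only assessments taken while fasting for 8 hours will be included in the baseline derivation". The protocol's own baseline rule (Section 9.4.1) carries no fasting condition, so this filter was introduced by the SAP.

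**Post-baseline selection.** SAP 3.8.1 maps assessments to visit windows and keeps the one nearest the target day, "irrespective of scheduled or unscheduled visit type". Fasting is not a criterion.

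**Analyses that use the selected values.** SAP 7.18 states: "The change from baseline in SHBG, LDL-c, will be analyzed in the same manner as specified in" Section 7.7, which is the ANCOVA. For safety chemistry and other laboratory results, SAP 8.3 says: "The change and percent change from baseline will also be summarized". SAP 8.3.5 adds shift tables from normal to abnormal. None of these sections mentions fasting.

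**Collection.** The Patient Fasting row of the protocol's Schedule of Activities reads: "Patients must be in fasted state for at least 8 hours prior to blood collection and treatment administration, where applicable". It is marked at Screening, at Weeks 0, 2, 4, 6, 8, 12 and 16, and at ET. Protocol 5.3.2 says of clinic attendance: "This includes at least an 8-hour fast prior to the visit, during which food and drink is restricted".

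**The concern.** The collection rule is the same throughout the study, but the analysis rule is not. A pre-dose glucose or lipid value taken without the fast is discarded, whereas a post-baseline value taken without it is analysed. For such a patient the change from baseline mixes the drug effect with the effect of having eaten.

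Lipids are a planned pharmacodynamic marker of THR-β agonism (Protocol 9.4.4.3). LDL increase and HDL decrease are named risks of FXR agonism (Protocol 2.3). Glucose is part of the chemistry panel, so it enters the change summaries and shift tables. Against a fasted-only baseline, an unfasted on-treatment glucose could appear as a treatment-period shift.

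**Working it through.** The plan states no figure on this point, so the check is mainly a comparison of rules.

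1. **Is fasting planned after baseline?** Yes. All nine columns of the Patient Fasting row are marked, and Protocol 5.3.2 draws no distinction between pre-dose and later visits.

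2. **Do the exempt draws matter?** No. Protocol 5.3.2 exempts only the sub-study draws at 48 and 72 hours after the Week 12 dose. Protocol Appendix 2 lists these as PK only ("48 hours ± 2 hours on Day 87" and the Day 88 draw). The 4- and 6-hour sub-study draws, after food may resume, contain PK, 7αC4 and FGF19 but no glucose or lipid panel.

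3. **Can an unfasted glucose or lipid value still arise?** Yes, in two ways. A patient may not comply at a scheduled visit, or an extra draw may be taken. The opening of Protocol Section 8 allows this: "Repeat or unscheduled samples may be taken for safety reasons or for technical issues with the samples". Protocol 8.1.9 asks for repeats within 48-72 hours of certain abnormalities, and Protocol 6.8.1 allows home visits.

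4. **What happens to it before dosing?** If Day 1 is unfasted and Screening was fasted, SAP 3.8.2 drops Day 1 and falls back to Screening.

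5. **What happens to it after dosing?** If the scheduled sample is the only one in the window, it is used as it stands. If there are two, the nearer one wins. As an illustration, the Week 12 chemistry window is Days 71-99 with target Day 85. A fasted scheduled visit on Day 82 (inside the ±3-day visit allowance) is |82 − 85| = 3 days away. An unfasted repeat on Day 84 is |84 − 85| = 1 day away. The repeat becomes the Week 12 value and the fasted sample is reclassified as unscheduled. The preference for scheduled samples applies only to exact ties.

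6. **Which analytes?** Glucose and HDL are in chemistry at all visits, and Table 4 has a chemistry row. The blinded lipid panel (LDL and others) is drawn on treatment at Weeks 2, 4, 6 and 12 and at ET, but not at Week 8 or Week 16. Table 4 has no row of its own for it. Displacement by an unscheduled draw is therefore clearest for glucose and HDL. An unfasted scheduled sample can affect any of them.

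7. **Does another rule catch it?** Not expressly. The major deviations listed in SAP 6.3 do not name non-fasting. The Per Protocol set is planned for MRI-PDFF and cT1 (SAP 7.8), while LDL-c is analysed on the efficacy set.

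8. **Size.** Let q be the unfasted fraction of an arm at a visit and D the fasted-unfasted difference. Assume D is constant and all 20 patients contribute.
   - Shift in arm mean change = q × D. One patient: 1/20 = 0.05 D. Three patients: 3/20 = 0.15 D.
   - Added variance = q(1 − q)D². One patient: 0.05 × 0.95 = 0.0475 D². Three patients: 0.15 × 0.85 = 0.1275 D².
   - Shift in the difference from placebo = (q_active − q_placebo) × D, which is zero in expectation if fasting compliance does not depend on treatment.

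   Neither q nor D is given in the documents, so none of these can be turned into mg/dL.

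**The case against.** A reader might infer from SAP 3.8.2 that post-baseline samples are taken in any state, so that the measurement condition is uncontrolled once dosing starts. The documents do not support this. The protocol demands the same fast at every visit, the lipid panel is drawn pre-dose, and no exempt draw contains glucose or lipids. The comparison is mismatched only when a sample breaks the rule or an extra draw is unfasted.

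A reader might also infer a biased comparison between arms. That goes too far as well. Patients are randomised, the study is double-blind, and post-baseline lipids other than HDL are withheld from sites. A shift common to all arms cancels against placebo, and a chance imbalance of a few patients is random error already reflected in the standard error.

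It can further be said that the baseline filter may serve only to choose among several pre-dose values. A later visit usually has one sample, so filtering there would create missing data. The SAP does not give its reason for the filter, so this reading is open. The missing-data point stands as a cost of the fix. It does not remove the gap, because the protocol's fasting rule covers Screening and Week 0 just as it covers later visits, and the SAP still filters only the former.

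**Conclusion.** The concern holds in a narrow form and is minor. As written, the SAP can set a fasted baseline against an unfasted post-baseline glucose or lipid value, and its visit-selection rule can prefer that value to a fasted one from the same window. The consequences are extra noise and a within-arm shift in exploratory PD and descriptive safety analyses. MRI-PDFF, cT1 and the incidence of treatment-emergent adverse events are unaffected.

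The size cannot be derived from the documents. In relative terms it is 5% of the fasted-unfasted difference per affected patient in an arm of 20. The absence of systematic between-arm bias rests on fasting compliance being unrelated to treatment, and nothing in the documents suggests otherwise.

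**What to change.** State in SAP 3.8.1 and 3.8.2 that, for glucose and lipid parameters, only samples taken after at least 8 hours' fasting are eligible for visit selection and for change-from-baseline summaries and ANCOVA, at baseline and post-baseline visits alike. Flag non-fasted values, and keep them in the listings and in every threshold-based safety count so that no safety signal is lost.

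The text change is one or two sentences, best made before unblinding so that the choice of values is not post hoc. Fasting status is already needed to apply the baseline rule. The team should confirm that it is recorded for post-baseline samples too.

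The cost is that a few post-baseline values leave the change analyses, with no fallback when the window holds no fasted sample: these analyses use observed data, and LOCF is planned only for the primary endpoint. Because the exclusion depends on behaviour after randomisation, add a supportive summary using all values to show whether it matters.
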